2.1. Study design

Study population

○ *Indication: Neuropathic pain*

○ *Dosage and administration: The usual starting dose in adults is 150 mg/day of pregabalin orally administered in 2 divided doses, which may be gradually increased to 300 mg/day over one week or longer. The dose may be adjusted depending on age and symptoms as*

appropriate, provided the daily dose may not exceed 600 mg and Lyrica should be orally administered in 2 divided doses regardless of the daily dose.

○ *Study population: The survey covers the patients satisfying all of the following requirements:*

- *Patients not participating in any other survey or study of Lyrica*
- *Patients never having used Lyrica before the survey*

Observation period

The observation period will start on the first day of treatment with Lyrica (Day 1) and last until Week 13 (Day 91). However, in cases where treatment has been completed or discontinued before Week 13, observation will be continued until completion (discontinuation) of treatment, and follow-up will be made for one week (7 days) after completion (discontinuation) of treatment.

During this survey, safety will be evaluated on the day of the first visit after the end of the observation period (including the last day of the observation period), as a rule. In cases where treatment has been completed or discontinued, safety will be evaluated until the day of the first visit following 7-day period after the completion (discontinuation) of treatment, and safety information will be collected for this period.

Completion of treatment means cases where further treatment with Lyrica is judged unnecessary because of achievement of the purpose of treatment set at the start of treatment (e.g., cure of target diseases).

Planned survey period

Survey period: January 2011 to April 2017

Registration period: January 2011 to January 2017 (-91 days from the survey period)

Target sample size and rationale

The target sample size is 3400 patients with neuropathic pain in total, including 3000 patients with peripheral neuropathic pain (1000 patients with postherpetic neuralgia, if possible, and 2000 patients with peripheral neuropathic pain of the types other than postherpetic neuralgia), and 400 patients with central neuropathic pain (300 patients with post-stroke pain, if possible, and other patients with pain following traumatic spinal cord injury and pain due to Parkinson's disease). For peripheral neuropathic pain, approximately 100 each of patients should be accumulated, if possible, for trigeminal neuralgia, peripheral entrapment neuropathy, iatrogenic neuropathy, neuropathy due to tumor-induced nerve compression or infiltration, posttraumatic pain, and chronic cauda equina syndrome.

The target sample size of 3400 patients with neuropathic pain is expected to have a 97% probability to detect adverse reactions occurring at the incidence of 0.1% or higher in at least 1 patient. Of the adverse reactions included in the major investigation items, vision-related events are anticipated to develop at the lowest incidence during the survey. In

clinical studies of Lyrica conducted in Japan and overseas, the lower bound of the 95% confidence interval for the incidence of this adverse reaction was 6.70% (incidence 7.40%, 380/5134 patients). If this adverse reaction develops at the same incidence as in these clinical studies, this reaction is expected to occur in 227 or more of 3400 patients. Since the safety and efficacy of Lyrica should be evaluated in patients with each type of neuropathic pain, enrollment of the following number of patients will be ensured; approximately 100 patients each, if possible, for trigeminal neuralgia, peripheral entrapment neuropathy, iatrogenic neuropathy, neuropathy due to tumor-induced nerve compression or infiltration, posttraumatic pain, and chronic cauda equina syndrome, approximately 300 patients for post-stroke pain, and a certain number of patients for pain following traumatic spinal cord injury and pain due to Parkinson's disease.

This sample size will also allow for adequate evaluation of the characteristics of other adverse reactions included in the major investigation items. The characteristics to be evaluated include time of onset and duration of adverse reactions, and these were also investigated in the clinical studies.

2.2. Study objective

The objective of this survey is to collect information on 1) adverse reactions that cannot be predicted from precautions for use (unknown adverse reactions), 2) the incidence of adverse reactions that will occur under actual use conditions, and 3) factors considered to affect safety, efficacy, etc. concerning the safety and efficacy of Lyrica in post-marketing routine clinical practice. At the same time, the necessity of conducting a special investigation or a post-marketing clinical study will be evaluated.

The following events will be evaluated as major investigation items;

- *Peripheral edema and edema-related events**
- *Dizziness, somnolence, loss of consciousness, syncope, and potential for accidental injury*
- *Vision-related events*

**: Adverse events of the cardiovascular and respiratory systems will also be checked.*

3. Interim and final analyses

Interim analyses for periodical safety report will be regularly performed in this survey. Interim analyses will be performed only for items necessary for periodical safety report as specified in this plan. In addition, the final analysis for the application for reexamination will be performed. At the final analysis, all analyses specified in this plan will be performed.

4. Hypothesis and decision rule

4.1. Statistical hypothesis

Because this survey is not a confirmatory investigation, the testing should be considered as exploratory in nature. Unless otherwise specified, the 2-sided testing is performed with a significance level of 5%.

4.2. Statistical decision rule

Not applicable.

5. Analysis sets

5.1. Safety analysis set

The safety analysis set is the full analysis set that is as close to all patients treated with Lyrica as possible. More specifically, the safety analysis set is defined as the population of registered or reported patients, excluding those who meet any of the following conditions.

- a. The survey form could not be collected at all (description in the report: “survey form not collected”).
- b. There was a contract violation or deficiency (description in the report: “contract violation/deficiency”).
- c. There was a registration violation (description in the report: “registration violation”).
- d. Administration of Lyrica under survey has not been reported at all (description in the report: “no administration information”).
- e. Information on adverse events has not been reported at all - no visits after the day of initial prescription (description in the report: “no adverse event information - no revisit”).
- f. Information on adverse events has not been reported at all - adverse events not described (description in the report: “no adverse event information - not described”).

Detailed handling of patient inclusion in/exclusion from the analysis set should be in accordance with patient inclusion/exclusion criteria separately specified.

5.2. Efficacy analysis set

The efficacy analysis set is defined as the population excluding patients meeting any of the following conditions from the safety analysis set.

- a. Efficacy evaluations have not been reported at all (description in the report: “no efficacy information”).
- b. Non-target disease of the survey (description in the report: “non-target disease”)

Detailed handling of patient inclusion in/exclusion from the analysis set should be in accordance with patient inclusion/exclusion criteria separately specified.

5.3. Other analysis sets

Not applicable.

5.4. Subgroups

Subgroup analyses of safety will be performed for the following patient demographics and other factors.

- Hepatic impairment
- Renal impairment
- Children (<15 years), adults (≥ 15 to < 65 years), elderly (≥ 65 years)
- Age [< 65 years, ≥ 65 to < 70 years, ≥ 70 to < 75 years, ≥ 75 to < 80 years, ≥ 80 to < 85 years, ≥ 85 years]
- Sex [male, female]
- Inpatient/outpatient status at the initial prescription [inpatient, outpatient]
- Body weight at the start of treatment (by sex) [< 40 kg, ≥ 40 to < 50 kg, ≥ 50 to < 60 kg, ≥ 60 kg]
- Name of target disease (i.e., diagnosis of neuropathic pain) [by disease name]
- Hemodialysis [no, yes]
- Creatinine clearance [< 15 mL/min, ≥ 15 to < 30 mL/min, ≥ 30 to < 60 mL/min, ≥ 60 mL/min]
- Past medical history [no, yes]
- Complications [no, yes]
- Prior medications [no, yes]
- Concomitant medications [no, yes]
- Non-medication therapies [no, yes]
- Timing of drug administration (at the start of treatment) [before meal, after meal, other]
- Daily dose (at the start of treatment) [≤ 25 mg, > 25 to ≤ 75 mg, > 75 to ≤ 150 mg, > 150 to ≤ 300 mg, > 300 to ≤ 600 mg, > 600 mg]
- Daily dose (maximum) [≤ 25 mg, > 25 to ≤ 75 mg, > 75 to ≤ 150 mg, > 150 to ≤ 300 mg, > 300 to ≤ 600 mg, > 600 mg]
- Pregnant and parturient women (pregnant)

Subgroup analyses of efficacy will be performed for the following patient demographics and other factors.

- Hepatic impairment
- Renal impairment
- Children (<15 years), adults (≥ 15 to < 65 years), elderly (≥ 65 years)
- Age [< 65 years, ≥ 65 to < 70 years, ≥ 70 to < 75 years, ≥ 75 to < 80 years, ≥ 80 to < 85 years, ≥ 85 years]
- Sex [male, female]

- Inpatient/outpatient status at the initial prescription [inpatient, outpatient]
- Body weight at the start of treatment (by sex) [<40 kg, ≥ 40 to <50 kg, ≥ 50 to <60 kg, ≥ 60 kg]
- Name of target disease (i.e., diagnosis of neuropathic pain) [by disease name]
- Hemodialysis [no, yes]
- Creatinine clearance [<15 mL/min, ≥ 15 to <30 mL/min, ≥ 30 to <60 mL/min, ≥ 60 mL/min]
- Past medical history [no, yes]
- Complications [no, yes]
- Prior medications [no, yes]
- Concomitant medications [no, yes]
- Timing of drug administration (at the start of treatment) [before meal, after meal, other]
- Daily dose (at the start of treatment) [≤ 25 mg, >25 to ≤ 75 mg, >75 to ≤ 150 mg, >150 to ≤ 300 mg, >300 to ≤ 600 mg, >600 mg]
- Daily dose (maximum) [≤ 25 mg, >25 to ≤ 75 mg, >75 to ≤ 150 mg, >150 to ≤ 300 mg, >300 to ≤ 600 mg, >600 mg]

Furthermore, subgroups will be defined based on initial dose (information on administration of Lyrica: dose on Day 1), and exploratory analyses will be performed in the safety analysis set and efficacy analysis set.

- Initial dose <150 mg, 150 mg, >150 mg

6. Endpoints and covariates

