## 5.4 Observation period

The observation period will start on the first day of treatment with the product (Day 1) and last until Week 13 (Day 91). However, in cases where treatment has been completed or discontinued before Week 13, observation will be continued until completion (discontinuation) of treatment, and follow-up will be made for one week (7 days) after completion (discontinuation) of treatment. During this survey, safety will be evaluated on the day of the first visit after the end of the observation period (including the last day of the observation period), as a rule. In cases where treatment has been completed or discontinued, safety will be evaluated until the day of the first visit following 7-day period after the completion (discontinuation) of treatment, and safety information will be collected for this period.

**Supplementary note:** Completion of treatment means cases where further treatment with the product is judged unnecessary because of achievement of the purpose of treatment set at the start of treatment (e.g., cure of target diseases).

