8.1.3. Analysis of binary data

Frequency and its proportion will be calculated. If the confidence interval of proportion is calculated, a 2-sided 95% confidence interval (exact method) will be calculated.

If the proportion is compared between subgroups, Fisher’s exact test and Cochran-Armitage test (exact method) will be performed for the relationships with nominal scale data and ordinal scale data, respectively, and the risk ratio and risk difference with their 95% confidence intervals will be calculated.

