For “peripheral edema and edema-related events”, number and proportion of patients with events will be tabulated by presence or absence of weight increase. Two types of definitions of patients with weight increase are used: 1) those with “weight increased (MedDRA PT)” reported as an adverse reaction; 2) those with body weight increased by 7% or more from baseline at least once. Number and proportion of patients with adverse reactions will be tabulated for each SOC and PT by presence or absence of peripheral edema. In addition, number and proportion of patients with the following adverse reactions will be tabulated by presence or absence of peripheral edema to evaluate the relationship between peripheral edema and cardiovascular and respiratory events.

- Events coded to the MedDRA PT “arrhythmia”, “atrial fibrillation”, “cardiovascular disorder”, “cardiac failure congestive”, “hypertension”, “hypotension”, “palpitations”, “tachycardia”, or “dyspnoea”
- Events coded to the MedDRA SOC “Cardiac disorders”, “Vascular disorders”, or “Respiratory, thoracic and mediastinal disorders”

For “dizziness, somnolence, loss of consciousness, syncope, and potential for accidental injury”, number of days to onset will be tabulated using more specific categories (≤ 4 weeks [1 to 28 days], 1 to 7 days, 8 to 14 days, 15 to 21 days, 22 to 28 days; >4 weeks [≥ 29 days], >4 to ≤ 13 weeks, >13 weeks). In addition, number and proportion of patients with adverse reactions will be tabulated by factor specified in Section 5.4. Tests specified in Section 8.1.3 will be performed to evaluate the relationship between patient demographics, etc. and development of adverse reactions.

Moreover, the median number of days to onset will be tabulated for the following adverse reactions.

- Dizziness
- Somnolence

^a: Occurrence of cardiovascular and respiratory events will be examined in patients with peripheral edema and edema-related events.

- Peripheral edema and edema-related events
- **Pancreas-related events, thyroidal function-related events, change in appetite and activity-related events, suicide-related events, withdrawal symptom and rebound phenomenon-related events, and skin disorder-related events**

Number and proportion of patients will be calculated for each event.

- **Patients with special background**

Number and proportion of patients with adverse reactions and serious adverse reactions will be calculated by SOC and PT in the following subgroups and other patients.

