8.2.3.4. Subgroup analysis

Number and proportion of patients with at least one adverse reaction will be tabulated by factor specified in Section 5.4. Tests specified in Section 8.1.3 will be performed to evaluate the relationship between patient demographics, etc. and development of adverse reactions. Furthermore, risk ratio and risk difference for the incidence of adverse reactions and their 95% confidence intervals will be calculated between subgroups.

In addition, number and proportion of patients with adverse reactions in each subgroup will be tabulated by SOC and PT for factors showing a significant difference by testing to evaluate the relationship between patient demographics, etc. and development of adverse reactions. Moreover, patient demographics, etc. (including breakdown of past medical history and complications, prior and concomitant medications) will be tabulated in each subgroup and number and proportion of patients with serious adverse reactions will be tabulated by SOC and PT in each subgroup as necessary.

Laboratory parameters will be tabulated as specified in Section 8.2.3.3 in patients whose target disease is painful diabetic neuropathy.

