10.2. Appendix 2: Details of statistical methods

A2.1 Subgroup analysis

Reference populations for calculation of risk ratio and risk difference in subgroup analyses of safety and efficacy are shown below.

Factor	Category	Reference population	Safety/ Efficacy
Special population			
Hepatic impairment	Yes, No	None	Safety, efficacy
Renal impairment	Yes, No	None	Safety, efficacy
Age	Children (<15 years), adults (≥15 to <65 years), elderly (≥65 years)	Adults (≥15 to <65 years)	Safety, efficacy
Patients demographics and others			
Sex	Male, female	Male	Safety, efficacy
Age	<65 years, ≥65 to <70 years, ≥70 to <75 years, ≥75 to <80 years, ≥80 to <85 years, ≥85 years	<65 years	Safety, efficacy
Inpatient/outpatient status at the initial prescription	Inpatient, outpatient	Outpatient	Safety
Body weight (by sex)	<40 kg, ≥40 to <50 kg, ≥50 to <60 kg, ≥60 kg	≥50 to <60 kg	Safety, efficacy
Name of target disease [by disease name]		N/A	N/A
Hemodialysis	Yes, No	None	Safety, efficacy
Creatinine clearance	<15 mL/min, ≥15 to <30 mL/min, ≥30 to <60 mL/min, ≥60 mL/min	≥60 mL/min	Safety, efficacy
Past medical history	Yes, No	None	Safety
Complications	Yes, No	None	Safety
Prior medications	Yes, No	None	Safety, efficacy
Concomitant medications	Yes, No	None	Safety, efficacy
Non-medication therapies	Yes, No	None	Safety
Timing of administration (at the start of treatment)	Before meal, after meal, other	After meal	Safety, efficacy
Daily dose (at the start of treatment)	≤25 mg, >25 to ≤75 mg, >75 to ≤150 mg, >150 to ≤300 mg, >300 to ≤600 mg, >600 mg	>75 to ≤150 mg	Safety, efficacy
Daily dose (maximum)	≤25 mg, >25 to ≤75 mg, >75 to ≤150 mg, >150 to ≤300 mg, >300 to ≤600 mg, >600 mg	>150 to ≤300 mg	Safety, efficacy

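### Adverse-reaction incidence is tested across categories of maximum daily dose, which the reaction and time on treatment can both change, so the result is not evidence of a dose effect

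*SAP*

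**What the plan says.** SAP 5.4 names maximum daily dose among the safety subgroup factors. It has six ordered categories, from "Daily dose (maximum) [≤ 25 mg" up to above 600 mg. The factor is then used as follows.

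- SAP 8.2.3.1, dizziness and somnolence item: "number and proportion of patients with adverse reactions will be tabulated by factor specified in Section 5.4", followed by the tests of 8.1.3.
- SAP 8.2.3.4: the same for patients with at least one reaction, and in addition "risk ratio and risk difference for the incidence of adverse reactions and their 95% confidence intervals will be calculated between subgroups". Appendix A2.1 makes >150 to ≤300 mg the reference. Reactions in each subgroup are then "tabulated by SOC and PT for factors showing a significant difference by testing".
- SAP 8.1.3: Fisher's exact test and "Cochran-Armitage test (exact method) will be performed for the relationships with nominal scale data and ordinal scale data, respectively". For ordered dose categories this is a trend test on proportions of patients.

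Nothing limits the maximum to doses taken before the reaction, and nothing allows for time on treatment. A pre-onset rule does exist elsewhere in 8.2.3.1: the tabulation by medication class leaves out concomitant drugs used after the first onset.

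On follow-up, Protocol 5.4 says that if treatment ends before Week 13, "follow-up will be made for one week (7 days) after completion (discontinuation) of treatment", and that "safety will be evaluated until the day of the first visit following 7-day period after the completion (discontinuation) of treatment".

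**The concern.** Maximum dose is a post-baseline quantity, and the documents describe two ways in which it can be tied to the outcome without any effect of dose.

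- **A reaction can stop titration.** Dose may be raised over a week or longer (Protocol 2). Protocol 5.3 says that events such as edema and dizziness were most frequent early in treatment. The actions recorded for a reaction include discontinuation, interruption and reduction (SAP 8.2.3.1). A patient who reacts early may therefore stay in a low category, and low categories fill with cases.
- **Early stopping for other reasons acts the opposite way.** Protocol 6.6 lists several such reasons. The patient loses both the chance of an increase and the time in which a reaction could be recorded, so low categories fill with short follow-up.

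Protocol 6.9 plans factor analysis by dose for each major investigation item, so readers are likely to take this table as evidence on dose. A significant test leads to further SOC/PT tables (SAP 8.2.3.4), and all planned analyses are run for the reexamination application (SAP 3). No caveat goes with them.

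**Working it through.** **The plan's own figures.** None concerns this comparison. The sample-size figures do reproduce: 1 − 0.999^3400 = 0.967 (stated 97%); exact lower 95% limit for 380/5134 = 6.70%; 3400 × 0.0670 = 227.8 (stated 227).

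**Inputs.** From the documents: N = 3400, incidence 7.4% (the vision-event rate), observation to Day 91, two-sided 5%. Titration, blocking and stopping rates are not given, so all are assumed. Ratios below are higher v lower maximum dose. With >150 to ≤300 mg as reference, the SAP's ratio for the lower category is the reciprocal.

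**1. Blocking, by hand, no dose effect.** Assume half the patients are intended for one increase, on a day uniform over 8–60. Assume 70% of onsets are uniform over Days 1–14 and 30% over Days 15–91.

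- Chance that onset falls on or before the increase day: early onsets (8 + 297/53)/14 = 0.972; late onsets (1081/53)/77 = 0.265. Overall 0.7 × 0.972 + 0.3 × 0.265 = 0.760.
- Cases among the 1700 intended for an increase: 1700 × 0.074 = 125.8. If half of the reactions that come first block the increase, 125.8 × 0.760 × 0.5 = 47.8 cases move to the lower group.
- Higher group: (125.8 − 47.8)/(1700 − 47.8) = 4.7%. Lower group: (125.8 + 47.8)/(1700 + 47.8) = 9.9%. Ratio 0.475.
- z = 0.0521/√[0.074 × 0.926 × (1/1652 + 1/1748)] = 5.8.
- If every such reaction blocks, 95.6 cases move: 30.2/1604.4 = 1.9% v 221.4/1795.6 = 12.3%, ratio 0.15.

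Simulation of the same model gave 0.475 and 0.151, with the trend test significant in 100% of runs.

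**2. Early stopping, same model, no blocking.** Follow-up ends at stopping. With half stopping early and 15% of onsets in Days 1–14, incidence was 5.1% v 6.4%, ratio 1.25, significant in 37%. With 70% of onsets early the ratio was 1.09 (10%). With neither mechanism the ratios were 1.00–1.02 (5–7%).

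**3. Both routes together.** A second simulation started everyone at 150 mg, with 60% intended for 300 mg on Days 8–28. The daily hazard was 1.5% (week 1), 0.4% (weeks 2–4) and 0.08% (later), and the 7 days after stopping were included. Other stopping of 0.5, 1 and 2% per day means 37, 60 and 84% stopped by Day 91 (for example 1 − 0.98^91 = 0.84). Ratios for 300 v 150 mg with a true hazard ratio of 1.0 (share significant by Fisher's test):

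| Reactions that block | No other stopping | 0.5%/day | 1%/day | 2%/day |
|---|---|---|---|---|
| 0% | about 1.0 | 1.06 (9–14%) | – | 1.19 (about 60%) |
| 10% | 0.88 | 0.95 | – | 1.08 |
| 30% | 0.70 (100%) | 0.75 (99%) | 0.79 (93%) | 0.85 (51%) |
| 80% | 0.36 (100%) | – | – | – |

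(– : cell not shown.) With a true hazard ratio of 1.5, the undistorted 13-week ratio would be 1.17. The maximum-dose ratio ran from 0.49 to 1.36, and at 30% blocking from 0.84 to 1.01.

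**4. Closer to the SAP: mixed starting doses, five dose categories, asymptotic Cochran-Armitage test.** Stopping is 0, 0.5 and 2% per day.

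- No true effect: a rising trend was significant in 2, 15 and 29% with no blocking. A falling trend was significant in 96, 80 and 23% at 30% blocking, and in 100% at 80% blocking.
- True ratio 1.5 per category: at 30% blocking the rise is attenuated but found in 98–99%. At 80% blocking it is found in 0, 1 and 19%, and significantly reversed in 49, 12 and 0%.

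**5. Current dose with time at risk.** In the model of step 3, a week-stratified Mantel-Haenszel rate ratio gave 0.99–1.01 for a true 1.0 and 1.48–1.52 for a true 1.5. If the hazard ends at stopping but the 7 days are counted at the last dose, it drifts to 1.05–1.07 and 1.58–1.61 at 2% per day. With frailty (gamma variance 1, titrated share 42% v 78%) it gave 0.64–0.68 and 0.93–0.99. The maximum-dose ratio then gave 0.25–0.81 and 0.33–0.92.

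**The case against.** **The plan claims no dose effect.** A reader might infer that the SAP presents this table as a dose–response finding. It does not: 8.2.3.4 speaks only of a relationship, 4.1 calls all testing exploratory, and 4.2 has no decision rule. This stands and limits the weight. The label deals with error rates and confirmatory status, however. It does not address bias, and with 3400 patients a biased ratio comes with a narrow interval.

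**The second route may be small.** SAP 5.1e excludes patients with no visit after the first prescription. With no blocking and 2% per day, removing everyone who stops before an assumed first visit on Day 7, 14 or 28 brings the ratio to about 1.04 (significant in 7%). This stands. It does not help with blocking: at 30% blocking the ratio moves from 0.85 to 0.74.

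**The tables are useful safety output.** A reader might infer that the tests should no longer trigger the SOC/PT tables. That goes too far, because the trigger in 8.2.3.4 is the only specified route to a SOC/PT breakdown by maximum dose.

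**The alternative is not clean.** Under frailty it invents an inverse effect or hides a real one. In one cell (no blocking, 2% per day, true 1.0) it gives 0.68, further from the truth than the maximum-dose ratio of 0.81. This stands and must be stated with any result.

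**The largest distortions need strong assumptions.** In the closer model, a true effect survives 30% blocking, and significant reversal is reported only at 80%. This also stands, although false falling trends under no effect appear at 30%.

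**Conclusion.** The point holds at modest weight. As written, the plan compares proportions by a dose that the reaction itself and time on treatment can change, with no rule or caveat for either. The result can hide, reverse or create a dose effect.

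A reader might infer that the table will show a falsely protective high dose. The documents do not support that: the two routes oppose each other, and no titration, blocking or stopping rates are given. Net direction and size are unknown, and every simulated figure above illustrates assumed inputs.

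The point concerns one listed factor in exploratory testing. Starting-dose comparisons avoid this mechanism, but they remain open to confounding, for example by renal function or age, and do not answer the question about dose after titration.

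**What to change.** 1. In SAP 8.2.3.1 and 8.2.3.4, keep the maximum-dose table and its SOC/PT breakdown as descriptive output. State that its tests, risk ratios and risk differences are not evidence of a dose effect, because maximum dose can be changed by the reaction and by time on treatment.
2. For the dose question, add an exploratory analysis by dose at or before first onset with time at risk: for example, event rates by current daily dose stratified by week of treatment, or Cox regression with time-dependent dose. Daily dose, dosing period (Protocol 6.2) and onset date (Protocol 6.8) are already collected. The SAP 8.2.2 dosing period includes interruptions, so count interruption days and the days after the last dose in a separate off-drug category.
3. State that this removes post-onset-dose and immortal-time bias but not confounding by tolerability or indication, and that under frailty it can still show a spurious inverse effect.
4. Leave the starting-dose comparisons as planned. Maximum dose is also an efficacy factor (SAP 5.4, 8.2.4.6) and is post-baseline there too, so a similar caveat can be added.

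The caveats cost only wording. The added analysis needs modest programming and must be labelled post hoc, because the SAP history records the survey as completed.
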